### **Inclusion and Exclusion Criteria**

Inclusion: a) Being physically inactive (not performing 300 or 150 min of moderate or vigorous intensity physical activity respectively per week measured with the IPAQ questionnaire); b) BMI between 25 and 39.9 kg/m^2; c) Belonging to the cardiovascular health program of the External CESFAM of Valdivia d) Presenting with or without non-oncologic chronic pain.

Exclusion: a) Bone disease; b) Ischemic disease or arrhythmia and c) Chronic respiratory disease d) Uncontrolled chronic diseases f) People unable to understand instructions, g) People who do not speak Spanish h) History of previous oncological disease or under study for suspected neoplastic disease in any part of the body i) Low adherence to training (< 70% or non-attendance at 4 continuous sessions).

Included users will be divided into 3 groups: HIIT, ERE, and Control. All subjects will be evaluated at four times: pre-intervention (week 0 – time 1), week 4 (time 2), week 8 (time 3), and post-intervention (week 12 – time 4). Only the evaluation of metabolic flexibility and direct oxygen consumption will be carried out pre (week 0) and post-intervention (week 12).

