### **Data Collection Techniques and Instruments**

Clinical Record Information Collection The following information will be obtained from each participant's clinical record:

- Sociodemographic Background: o Gender o Age o Ancestry o Education
- Medical Background o Time within the cardiovascular health program o Morbid history o Medications and dosage o Time using medications o Laboratory tests (fasting glucose, glycosylated hemoglobin, lipid profile)

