### **Physical Activity Level and Quality of Life**

The international physical activity questionnaire (IPAQ) (40) will be applied to estimate the level of physical activity prior to the intervention. Health-related quality of life will be measured using the SF36 questionnaire (41) before and after the intervention.

Physical Function Physical function will be measured through the Six-Minute Walk Test, and grip dynamometry.

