## **Metabolic Parameters**

Fasting glucose, cholesterol, and triglyceride values will be obtained through tests requested in the controls of the Cardiovascular Health Program.

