## **Adaptation Capacity to Workload**

The capacity to adapt to workloads will be evaluated through the changes observed in the tests described above at four times: pre-intervention, week 4, week 8, and post-intervention (week 12).

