## **Statistical Analysis**

The sample size will be calculated as follows: (1) ANOVA for repeated measures with intra-inter-group interaction, (2) three groups, (3) type I error: 5%, (4) type II error: 20%, (5) statistical test power: 80%, and (6) effect size (ES): 0.10 according to Cohen's classification (1988). Using these parameters, the total sample size recommended by G\*Power software (Version 3.1.9.2) was 174 (58 per group). Assuming a 10% dropout, the total was calculated at 192, with 64 participants randomly assigned to each group. The concealment of allocation will be conducted by a researcher not involved in the clinical procedures of the intervention using the

method of opaque, sealed, and consecutively numbered envelopes. The random sequence and allocation concealment allow for the control of selection bias.

For enhanced bias control, the data analysis will be performed by a researcher blinded to the intervention groups. Dependent variables will be described in terms of mean and standard deviation. Assumptions of normality and homoscedasticity for all data will be verified using the Shapiro-Wilk test and the Levene's test, respectively. To address General Objective 1, the Student's t-test will be used to detect baseline differences between groups, and a repeated measures ANOVA (group x time) to determine differences in all dependent variables between training prior, and at 4, 8, and 12 weeks afterwards. The Bonferroni post hoc test will be used to test differences between groups. Additionally, the Cohen's d test will be applied to determine the effect size. To address the General Objective, the Pearson correlation test will be used to determine the relationship between MHR and the presence and intensity of non-oncological chronic pain. The level for statistical significance was set at  $p < 0.05$ . Statistical analyses will be performed using SPSS software version 21 (SPSS™ Inc., Chicago, IL, USA).

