## **Month 3**

- Pre-intervention evaluation (IPAQ, SF36, Cardiometabolic Variables, Metabolic Flexibility, and Pain)
- Exercise familiarization

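### The four-visit group x time ANOVA cannot be fitted to metabolic flexibility, oxygen consumption or SF-36, which are measured only before and after, and the plan names no other analysis for them

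*Combined protocol and SAP*

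**What the plan says.** **Analysis.** Under Statistical Analysis, General Objective 1 is addressed by a repeated-measures group x time ANOVA "to determine differences in all dependent variables between training prior, and at 4, 8, and 12 weeks afterwards". No other model is named for comparing groups over time. Dependent variables is not defined. Objectives 1, 1.1 and 1.2 name cardiometabolic risk factors, physical function and pain.

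**Schedule.** Under Inclusion and Exclusion Criteria, "All subjects will be evaluated at four times" (weeks 0, 4, 8 and 12), with one stated exception: "Only the evaluation of metabolic flexibility and direct oxygen consumption will be carried out pre (week 0) and post-intervention (week 12". Under Physical Activity Level and Quality of Life: "Health-related quality of life will be measured using the SF36 questionnaire (41) before and after the intervention". Adaptation Capacity to Workload is "evaluated through the changes observed in the tests described above at four times".

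**Work plan.** Month 3 has "Pre-intervention evaluation (IPAQ, SF36, Cardiometabolic Variables, Metabolic Flexibility, and Pain". The four-weekly list for Months 4, 5 and 6 runs to week 12 and contains only cardiometabolic variables and pain. Month 7 contains no assessment.

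**Laboratory values.** Metabolic Parameters: "Fasting glucose, cholesterol, and triglyceride values will be obtained through tests requested in the controls of the Cardiovascular Health Program". Data Collection Techniques and Instruments takes "Laboratory tests (fasting glucose, glycosylated hemoglobin, lipid profile" from the clinical record. Glycosylated hemoglobin is in that list but not under Metabolic Parameters.

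**Sample size.** Repeated-measures ANOVA with within-between interaction, three groups, 5% type I error, 80% power, effect size 0.10, giving 174 (58 per group), raised to 192 for 10% dropout.

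**The concern.** Three outcomes have no week 4 or week 8 value, so the analysis as written cannot be run on them and the analyst must choose a substitute. SF-36 is one of them, and Expected Results anticipates better quality of life, so a result is intended. A two-level group x time ANOVA and a baseline-adjusted comparison differ in power, and they can differ in result when the groups differ at baseline. The plan tests for baseline differences, so the choice should be fixed before those tests are seen.

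For glucose and lipids the question is whether dated values will exist at weeks 4 and 8. If they do not, a four-visit ANOVA needing complete series would drop participants or use results that do not belong to the visit.

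**Working it through.** **1. Visits by outcome**

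| Outcome | Visits in the methods text | Work plan |
|---|---|---|
| Metabolic flexibility | Weeks 0 and 12 | Month 3 only |
| Direct oxygen consumption | Weeks 0 and 12 | Not listed by name |
| SF-36 | Before and after | Month 3 only |
| Physical function | Four visits | Not listed by name |
| Glucose, lipids | Four visits nominally; source is programme tests and the clinical record | Cardiometabolic variables, Month 3 and four-weekly |

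The first three cannot carry a four-level time factor. The work plan does not settle the schedule. It shows no post-intervention SF-36 or metabolic flexibility, which disagrees with the methods text, and it omits physical function, an Objective 1 outcome, so its lists are not exhaustive.

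**2. The plan's own sample size**

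The number of occasions m, correlation rho and sphericity factor epsilon are not stated. With k=3 groups, f=0.10 and epsilon 1:
- lambda = f² x N x m / (1 - rho), df1 = (k-1)(m-1), df2 = (N-k)(m-1).
- With m=4, rho=0.5, N=174: lambda = 0.01 x 174 x 4 / 0.5 = 13.92, df 6 and 513, power 80.4%. N=171 gives 79.6%.

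So 174 is the smallest multiple of three that reaches 80% under four occasions, rho 0.5 and epsilon 1.

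**3. Week-12 differences implied by f=0.10 over four visits**

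Assume both exercise groups differ from control by d SD at week 12. The group part of the interaction sum of squares is 58 x d² x (1/9 + 1/9 + 4/9) = 38.67 d². The time part, S, is the sum of squared deviations of the time profile from its mean. The total must equal f² x N x m = 6.96, so d² = 6.96 / (38.67 S) = 0.18 / S.

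| Assumed time course | Profile at 0, 4, 8, 12 | S | d |
|---|---|---|---|
| Change between weeks 4 and 8 | 0, 0, 1, 1 | 1 | 0.42 |
| Plateau from week 4 | 0, 1, 1, 1 | 0.75 | 0.49 |
| Change only at week 12 | 0, 0, 0, 1 | 0.75 | 0.49 |
| Linear | 0, 1/3, 2/3, 1 | 0.556 | 0.57 |

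**4. Two candidate analyses for the two-visit outcomes, N=174**

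- Two-level group x time ANOVA: lambda = 38.67 d² x 0.5 / (1 - rho), df 2 and 171.
- Week-12 ANCOVA on baseline: lambda = 38.67 d² / (1 - rho²), df 2 and 170.

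Example at d² = 0.18 and rho 0.5: 38.67 x 0.18 = 6.96. The ANOVA lambda is 6.96 x 0.5 / 0.5 = 6.96, and the ANCOVA lambda is 6.96 / 0.75 = 9.28.

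| d (assumed) | rho (assumed) | ANCOVA | Two-level ANOVA |
|---|---|---|---|
| 0.42 | 0.3 | 69% | 49% |
| 0.42 | 0.5 | 78% | 64% |
| 0.42 | 0.7 | 92% | 87% |
| 0.49 | 0.5 | 89% | 78% |
| 0.57 | 0.5 | 96% | 89% |

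Simulation of the 0.42 SD rows (4,000 runs each) agrees: ANCOVA 0.687, 0.768 and 0.916; ANOVA 0.486, 0.642 and 0.865 at rho 0.3, 0.5 and 0.7. The variance of the ANCOVA comparison relative to the change-score comparison is (1 + rho)/2, that is 0.65, 0.75 and 0.85.

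**5. Laboratory values**

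The documents give no test frequency, so no loss can be computed.

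**The case against.** **Scope.** The ANOVA is introduced for General Objective 1, which does not name metabolic flexibility, oxygen consumption or SF-36. On that reading nothing conflicts. This stands as a reading, but it leaves three scheduled measurements without any analysis, which is also a gap.

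**The default is obvious.** The plan names one model family, so the natural reading is the same ANOVA on the visits available. That is fair, and it would remove the conflict. ANCOVA is therefore an improvement on the default, not the only cure.

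**The gain depends on the assumptions.** Also fair. The difference d, the equal-effect pattern and rho are all assumed, and 0.42 SD is the low end of the range. At 0.57 SD and rho 0.5 both analyses exceed 80%.

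**Stronger readings the documents do not support.** A reader might infer that the two-visit outcomes are underpowered compared with the four-visit ones. That depends on rho and the time course: at rho 0.5 the two-level ANOVA gives 64% to 89% against 80% for four visits. A reader might take the work plan as confirming the pre/post schedule; it does not, because it shows no post-intervention measurement of SF-36 or metabolic flexibility. A reader might infer that laboratory values will be missing at weeks 4 and 8. Nothing says tests will not be requested then; the source is unsecured, which is short of a contradiction. Nor do the unstated sample-size inputs make 174 wrong. It reproduces, and their absence is a reporting gap.

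**Conclusion.** The point holds for metabolic flexibility, direct oxygen consumption and SF-36: the four-level model cannot be fitted to them, or, on the narrow reading of scope, no analysis is stated. Confidence in this is high because it rests on the schedule text alone.

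The size of the issue is the power lost by falling back on a two-level ANOVA when the baseline needed for ANCOVA is already collected. At rho 0.5 the loss is about 14, 11 and 7 percentage points (78 - 64, 89 - 78, 96 - 89) for 0.42, 0.49 and 0.57 SD. At 0.42 SD it is 20 points at rho 0.3 (69 - 49) and 5 at rho 0.7 (92 - 87). These figures assume equal effects in both exercise groups and 174 participants with both measurements.

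The laboratory point is secondary and unquantified. It should be changed before data are seen, but it does not put the trial's design in doubt.

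**What to change.** 1. In Statistical Analysis, limit the four-visit ANOVA to outcomes measured at all four visits, and list them. Analyse metabolic flexibility, oxygen consumption and SF-36 by week-12 ANCOVA adjusted for the baseline value. A two-level group x time ANOVA would also be coherent, with less power.
2. Add SF-36 to the pre/post exception under Inclusion and Exclusion Criteria. Reconcile the work plan with the methods text, showing post-intervention SF-36 and metabolic flexibility and the physical function assessments.
3. Reconcile Metabolic Parameters and the clinical-record list with the four-weekly schedule, say whether glycosylated hemoglobin is an outcome, and record test dates. If tests are not obtained at each visit, use the results closest to weeks 0 and 12 within a window fixed before data are seen, analyse by ANCOVA on baseline, and report by group how many have no result in the window.
4. State the number of occasions, rho and epsilon behind 174.

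**Cost.** Protocol and SAP wording, plus recording of laboratory dates; items 1, 2 and 4 need no added visits. The downside of the window in item 3 is some missing laboratory values and no laboratory analysis at weeks 4 and 8. Obtaining tests at each visit instead could mean extra tests.

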## **Specific**

- Objective 1.1: Analyze the effects of a 12-week HIIT and ERE program on the workload adaptation capacity in cardiometabolic risk factors, physical function, and non-oncologic chronic pain in users of the Cardiovascular Health Program at the External CESFAM of Valdivia.
- Objective 1.2: Compare the effects of a 12-week HIIT and ERE program on the workload adaptation capacity in cardiometabolic risk factors, physical function, and non-oncologic chronic pain in users of the Cardiovascular Health Program at the External CESFAM of Valdivia.
- Objective 2.1: Determine the relationship between the number of cardiovascular risk factors and the presence of non-oncologic chronic pain in users of the PSCV at the External CESFAM of Valdivia.
- Objective 2.2: Determine the relationship between the number of cardiovascular risk factors and the intensity of non-oncologic chronic pain in users of the PSCV at the External CESFAM of Valdivia.
- Objective 2.3: Associate the presence of non-oncologic chronic pain with other chronic diseases.

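### Bonferroni is valid for the HIIT–ERE comparison of Objective 1.2 but conservative: at a 0.4 SD gap a closed three-group procedure would add about 4 to 17 points of power at the same familywise error

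*Combined protocol and SAP*

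**What the plan says.** Specific Objective 1.2 is to "Compare the effects of a 12-week HIIT and ERE program on the workload adaptation capacity", so a head-to-head comparison of the two exercise arms is an aim in its own right. There are three groups, and for most measures "All subjects will be evaluated at four times: pre-intervention (week 0", then weeks 4, 8 and 12).

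The Statistical Analysis section sizes the trial for "ANOVA for repeated measures with intra-inter-group interaction, (2) three groups", with "effect size (ES): 0.10 according to Cohen's classification (1988") and "statistical test power: 80"%. This gives 174 participants, 58 per group, raised to 192 for dropout. The analysis is a group × time repeated measures ANOVA on every dependent variable. For comparisons among the groups the only provision is: "The Bonferroni post hoc test will be used to test differences between groups".

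The section does not give a HIIT–ERE effect, a power for that pair, a primary outcome, a primary time point or the size of the Bonferroni family. It does not say that the post hoc test depends on a significant ANOVA.

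**The concern.** The stated 80% belongs to a three-group interaction test. Objective 1.2 rests on one pair, which under Bonferroni over three pairs is tested at 0.05/3 = 0.0167. With exactly three groups that penalty is larger than error control requires. If the three group means are not all equal, at most one of the three pairwise null hypotheses can still be true. A valid three-group test at 5% therefore protects the case where all three are equal, and each pair can then be tested at the full 5%. This is the closed testing principle.

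The stake is efficiency. A real difference between the two programmes is more likely to be missed than it need be, and a reader may take the 80% to describe a comparison it does not cover.

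**Working it through.** **Inputs.** From the plan: three groups, 58 analysable per group, four visits, 5% type I error, f = 0.10. Assumed, because the plan is silent: two-sided tests, a Bonferroni family of three pairs, correlation 0.5 between visits and sphericity. Gaps are in SD units of the contrast analysed; the plan gives no HIIT–ERE gap, so 0.4 SD is illustrative.

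**1. The plan's own figure.** For the group × time interaction, λ = f²·N·m/(1−ρ) = 0.01 × 174 × 4 / 0.5 = 13.92, with df1 = (3−1)(4−1) = 6 and df2 = (174−3)(4−1) = 513. Power is 0.804, so 174 reproduces. The 80% therefore belongs to this 6-df test.

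**2. The ceiling on the loss.** For one pair with standardised shift θ, power is about Φ(θ − 1.960) at 0.05 and Φ(θ − 2.394) at 0.05/3. The difference is largest midway between the two critical values: 2Φ((2.394 − 1.960)/2) − 1 = 2Φ(0.217) − 1 = 0.172. It is 17.2 points where unadjusted power is 60%, 14.2 at 80% and 9.8 at 90%. This is a ceiling because the test at 0.05 here has no gate in front of it.

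**3. The gain from the procedure itself.** For 58 per arm and a gap of 0.4 SD, θ = 0.4 × √(58/2) = 2.154. Bonferroni power is about Φ(2.154 − 2.394) = Φ(−0.240), or 40%. Simulated HIIT–ERE power, with the gate (2-df three-group F test at 5%) included:

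| Position of control | Bonferroni | Closed | Gain (points) |
|---|---|---|---|
| Midway between the exercise arms | 39.6% | 44.2% | 4.6 |
| Equal to one exercise arm | 39.8% | 49.6% | 9.8 |
| Below both (means 0.6/0.2/0 SD) | 39.9% | 55.8% | 15.9 |
| Below both (means 0.8/0.4/0 SD) | 40.0% | 57.3% | 17.3 |

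In the last two rows Holm gives 46.2% and 51.2%. At a larger gap of 0.52 SD, Bonferroni gives about 65% and the closed procedure 69% to 80%, again depending on control.

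**4. Familywise error.**

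| True state | Bonferroni | Closed |
|---|---|---|
| All three equal | 0.044 | 0.051 |
| HIIT = ERE, control 0.3 SD lower | 0.017 | 0.041 |
| HIIT = ERE, control 0.6 SD lower | 0.016 | 0.050 |
| HIIT = ERE, control 2 SD lower | 0.017 | 0.051 |

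The closed procedure stays at 5% within simulation error. Bonferroni leaves about two thirds of the allowance unused when one pair is null: (5 − 1.7)/5 = 66%.

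**5. The gate must test the same contrast.** With group differences placed only at weeks 4 and 8, so that no pair differs in change from week 0 to week 12, pairwise tests at 5% on that change had these familywise errors: 0.119 when gated by the 6-df group × time test, 0.050 when gated by the 2-df test of the same change, and 0.044 with Bonferroni. The interaction test can be significant for reasons unrelated to week 12, so it does not protect week-12 pairs.

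**The case against.** **Bonferroni is a legitimate choice.** It controls error, needs no gate and comes with matching simultaneous confidence intervals, which the closed procedure gives up. This stands: the point is lost efficiency, and a reader who inferred that the planned analysis is wrong would go beyond the documents.

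**The 17 points are not general.** A reader might take 17 points as the cost of Bonferroni here. It is the maximum, reached only when control lies well below both exercise arms and unadjusted power is near 60%. The plan gives no pairwise effects, so it cannot support a single figure. The Expected Results section anticipates improvement with training and the Control Group section asks controls to keep their habits, so control below both arms is the natural ordering to expect. It is not a stated assumption.

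**The planned ANOVA might seem to be the gate already.** The documents do not say so, and step 5 shows that it would not control error for week-12 pairs.

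**The omnibus effect does not fix the pair effect.** An interaction f of 0.10 is compatible with any HIIT–ERE effect down to zero, when the two exercise arms are equal and differ only from control. No pairwise power follows from the sample size calculation.

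**Week 12 alone is not the adaptation question.** The Adaptation Capacity to Workload section defines the target as change over four visits. This stands, and is why the comparison should be added to the four-visit analysis and not replace it.

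**Conclusion.** The point holds as an efficiency gain that is worth taking. In every configuration tried, the closed procedure beat Bonferroni for HIIT versus ERE and kept familywise error at 5% within simulation error, with no extra participants or visits. At 58 per arm and a 0.4 SD gap the gain is about 4 to 5, 10, or 16 to 17 points, depending on whether control lies midway between, level with one of, or below both exercise arms.

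This assumes two-sided tests, a family of three pairs, normal outcomes with equal variance, and one named contrast per outcome. The correlation of 0.5 and sphericity matter only for reproducing the 174 and for the check on the interaction gate. Neither procedure controls error across the many dependent variables, for which the plan names no primary outcome. That larger gap exists now, and this change does not close it.

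**What to change.** In the Statistical Analysis section:

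- Keep the four-visit group × time ANOVA as planned.
- For Objective 1.2, add a pre-specified baseline-adjusted week-12 comparison for each outcome: a three-group (2-df) test at 5% and, only if it is significant, each pair at 5%.
- State that the gate is the three-group test of that same week-12 contrast and not the 6-df group × time interaction.
- For group comparisons at weeks 4 and 8, replace Bonferroni by Holm, which never rejects less, and state the family (three pairs at each visit).
- State that the 80% power applies to the three-group interaction and not to HIIT versus ERE.

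The cost is a few sentences fixed before the data are seen, one added model per outcome, and a commitment to week 12 as the time point for Objective 1.2. There are no matching simultaneous confidence intervals; report unadjusted intervals and label them as such. The text should also acknowledge that error across outcomes remains uncontrolled, as it is under the present plan.

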Generally, the results of exercise programs show the final changes after an intervention, leaving aside the capacity for adaptation to workload during the intervention. The processes of adaptation to exercise are studied mainly in athletes; however, little is known about the adaptability capacity, in special populations, regarding CRFs, metabolic flexibility, physical function, and non-oncologic chronic pain, specifically in users belonging to the Cardiovascular Health Program of the External CESFAM of Valdivia, subjected to two types of exercise.

Despite knowing the link between non-oncologic chronic pain and the presence of cardiovascular diseases, the individual relationship between different cardiovascular risk factors and pain intensity is still uncertain.

Thus, implementing a physical exercise program associated with the PSCV will improve the possibility of controlling CRFs, improving metabolic flexibility, reducing non-oncologic chronic pain, and promoting lifestyle change difficult to achieve in users of this cohort. On the other hand, the External CESFAM will be recognized as a pioneering establishment in the implementation of non-pharmacological alternatives (personalized and expert-guided physical exercise) to improve the health and quality of life of PSCV users, which will not generate extra costs to the establishment for its application.

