## **Objectives**

### **General**

- Objective 1: Evaluate the effects of a 12-week HIIT and ERE program on the workload adaptation capacity in cardiometabolic risk factors, physical function, and non-oncologic chronic pain in users of the Cardiovascular Health Program at the External CESFAM of Valdivia.
- Objective 2: Determine the relationship between cardiovascular risk factors and non-oncologic chronic pain in users of the Cardiovascular Health Program at the External CESFAM of Valdivia.

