## **High-Intensity Interval Training (HIIT)**

During HIIT, 8-10 intervals/session will be performed on a cycle ergometer, at an intensity of 80-100% of the theoretical maximum heart rate (MHR) according to Karvonen, equating to a bicycle load of 8 to 10 points on the modified Borg scale of 1-10 points (55). Each interval will consist of 1 minute of cycling, followed by 2 minutes of inactive rest, similar to previous protocols (27). Every two weeks, the bicycle load will be adjusted (increasing the resistance to pedaling of the bicycle) due to normal physiological adaptations and improvement of the patient's baseline threshold, always exercising the patient in each effort interval at a muscular intensity of 8 to 10 points according to the modified Borg scale similar to previous studies (27).

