## **Expected Results**

Following the training application, we expect that the measured variables will modify their values on average in favor of greater adaptation to workloads, improved health condition, better quality of life, and a reduction in the pharmacological arsenal used before the intervention. Additionally, implementing a physical exercise program associated with the PSCV will improve the possibilities of controlling MHR and promote lifestyle changes in users of this population. Moreover, the CESFAM Externo will be showcased as a pioneering establishment in the implementation of non-pharmacological alternatives (personalized physical exercise and guided by experts in physical exercise and health) to improve the health and quality of life of PSCV users, which will not generate extra expenses for its application. On another front, the results obtained during the intervention could be published in press articles, congresses, and scientific journals to disseminate the good practices carried out by CESFAM and the Universidad San Sebastián.

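### The analysis sentence for General Objective 2 names MHR instead of the number of cardiovascular risk factors, and it names no visit

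*Combined protocol and SAP*

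**What the plan says.** Under Objectives (General), the second of the two general objectives is to "Determine the relationship between cardiovascular risk factors and non-oncologic chronic pain in users of the Cardiovascular Health Program". The Specific objectives make the exposure a count. Objective 2.1 is to "Determine the relationship between the number of cardiovascular risk factors and the presence of non-oncologic chronic pain" and Objective 2.2 is to "Determine the relationship between the number of cardiovascular risk factors and the intensity of non-oncologic chronic pain".

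Statistical Analysis first covers General Objective 1. It then gives one further sentence, introduced as addressing the General Objective without a number: "the Pearson correlation test will be used to determine the relationship between MHR and the presence and intensity of non-oncological chronic pain". No other sentence in that section deals with risk factors and pain, and the number of risk factors is not mentioned there.

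The abbreviation is expanded only in the HIIT section, where training intensity is set at "80-100% of the theoretical maximum heart rate (MHR) according to Karvonen". The abbreviation for cardiovascular risk factors, introduced in the Problem Statement, is CRFs.

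Inclusion and Exclusion Criteria sets evaluations at weeks 0, 4, 8 and 12. The Work Plan places cardiometabolic variables and pain at the pre-intervention evaluation (Month 3) and every four weeks to week 12 (Months 4, 5, and 6). The correlation sentence does not say which of these visits it uses.

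**The concern.** There are two gaps in one sentence, and it is the only rule for one of the two general objectives.

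- **Variable.** Read with the document's own expansion, the sentence correlates maximum heart rate with pain. That does not answer Objective 2, 2.1 or 2.2. Maximum heart rate is a real quantity in this trial, because it sets HIIT intensity, so an analyst could carry out the sentence literally.
- **Visit.** Correcting the abbreviation still leaves four candidate visits. After week 0, two of the three groups are in programmes that the plan expects to change the measured variables (Expected Results). Low adherence to training is also listed as an exclusion. A later visit could therefore mix the association between risk factors and pain with the effect of training, in a selected sample. An unstated visit also leaves room to choose once the data are seen.

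**Working it through.** **1. Which variable is meant.** The sentence carries no objective number, so it is assigned by content: General Objective 1 is dealt with just before it, and presence and intensity of pain are the outcomes of Objectives 2.1 and 2.2.

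| Place | Exposure named |
|---|---|
| Objectives, General (Objective 2) | cardiovascular risk factors |
| Objectives, Specific (2.1, 2.2) | number of cardiovascular risk factors |
| Statistical Analysis | MHR |
| HIIT section | MHR expanded as theoretical maximum heart rate |

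Two near-parallel sentences show the likely cause. The Problem Statement says that an exercise programme linked to the cardiovascular programme "will improve the possibility of controlling CRFs". Expected Results says that it "will improve the possibilities of controlling MHR and promote lifestyle changes in users of this population". The second makes sense only if MHR stands for risk factors.

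**2. The plan's own figures.** No sample size is stated for the correlation. The stated 174 belongs to the group-by-time ANOVA and reproduces with 3 groups, m = 4 visits and f = 0.10, assuming a correlation between visits ρ = 0.5 and sphericity (neither is stated):

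- λ = f²·N·m/(1 − ρ) = 0.01 × 174 × 4/0.5 = 13.92, with 6 and 513 degrees of freedom; power is 0.804 (0.796 at N = 171).
- Dropout: 58 × 1.10 = 63.8, rounded up to 64 per group, or 192 in total.

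Neither figure depends on the correlation sentence. For context, the smallest correlation detectable with 80% power (two-sided 5%) is tanh[(1.960 + 0.842)/√(n − 3)], which is 0.20 at n = 192 and 0.21 at n = 174.

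**3. What the choice of visit could do.** Inputs from the documents: the share allocated to training is p = 128/192 = 2/3, and 174 remain after dropout. Assumptions: count and pain are unrelated within groups, and training lowers each by the same d standard deviations. Pooling the groups then induces

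r = p(1 − p)d² / [1 + p(1 − p)d²], with p(1 − p) = 2/9.

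The rejection rate uses the Fisher z approximation at n = 174. The simulation used 58 control and 116 trained participants and 10,000 runs.

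| d (SD, both variables) | Induced r | Rejection rate | Simulation |
|---|---|---|---|
| 0.2 | 0.009 | 5.2% | 5.1% |
| 0.5 | 0.053 | 10.6% | 10.6% |
| 0.8 | 0.125 | 37.3% | 38.1% |

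At week 0 the rate is the nominal 5%. If the two shifts differ, the numerator becomes p(1 − p)·d₁·d₂. If the count does not move (d₁ = 0), the induced correlation is zero at any visit.

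**4. Whether week 0 data can be used as they stand.** Cardiometabolic variables and pain are scheduled at week 0. However, glucose, cholesterol and triglycerides come from tests requested at programme controls (Metabolic Parameters), and laboratory results are taken from the clinical record (Clinical Record Information Collection). Neither place gives a date relative to week 0. No section lists the conditions that make up the count.

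**The case against.** The strongest reply is that this is an editorial slip whose meaning can be recovered. No objective, measurement section or work-plan item treats maximum heart rate as a study variable, and the parallel sentences show what was intended. That stands as an explanation. A reader might infer from the sentence that a heart-rate analysis is really planned, or that Objective 2 will lose most of its power. The documents do not support either: they give no correlation between maximum heart rate and the risk-factor count, so no power loss can be calculated. What remains is that the slip sits in the analysis rule itself.

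On the visit, the reply is that week 0 is the natural reading. Objective 2 mentions no intervention, and having or not having pain is an entry characteristic. The count may rest largely on diagnoses in the clinical record, which need not change in 12 weeks, and control participants do not train. All of this is fair. A reader might infer that an analysis at week 4, 8 or 12 would necessarily be biased. That goes too far: the calculation shows almost nothing at 0.2 SD, and nothing at all if the count is fixed. Because the plan does not say how the count is formed, it does not settle which case applies.

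Nothing here challenges the choice of Pearson correlation or the randomised comparison.

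**Conclusion.** The point holds, within limits. As written, the only analysis rule for General Objective 2 names the wrong variable and no visit. The wrong variable is a matter of text and needs no assumption; it is very probably an abbreviation error.

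The consequence of the missing visit is conditional. It requires training to shift both the count and pain, it is negligible for small shifts, and it is absent if the count rests on recorded diagnoses. The larger rates in the table depend on assumed equal shifts of 0.5 or 0.8 SD, for which the documents give no support either way. Stating week 0 is therefore an inexpensive safeguard, not the repair of a demonstrated bias. The General Objective 1 analysis and the sample size of 192 stand as they are.

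**What to change.** In Statistical Analysis, replace the sentence with wording such as:

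> For General Objective 2, the association of the number of CRFs with the presence and with the intensity of non-oncologic chronic pain will be assessed by Pearson correlation, using week 0 data from all enrolled participants.

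Add beside it:

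- the list of conditions counted as CRFs, and the source of each (clinical record, measurement or laboratory test);
- a date window around week 0 for laboratory values taken from programme controls.

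In Expected Results, change MHR to CRFs.

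The cost is one rewritten sentence, a short definition and one abbreviation. No visit or measurement is added, since week 0 already includes cardiometabolic variables and pain. The one practical consequence is that some programme laboratory values may fall outside the window, so the team should check their timing before fixing it.
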